#### 6.12.4.3. Injection Site Reaction

The injection site reactions will be searched by MedDRA PTs from all TEAEs. The number and percentage of patients experiencing treatment-emergent injection site reaction will be summarized and compared by treatment group using Fisher's exact test.

For injection site reactions, the presence and severity of erythema, induration, pain, pruritus, and edema were collected through the eCRF, and will be summarized for each treatment. There will be no statistical comparison between treatments.

#### 6.12.4.4. Hepatobiliary Events

#### 6.12.4.4.1. Treatment-Emergent Potential Hepatic Disorder

The percentages of patients with treatment-emergent drug-related hepatic disorder events will be summarized and compared by treatment group using MedDRA PT nested within each SMQ ordered by decreasing frequency. The following SMQs based on MedDRA will be used to identify potential hepatic disorders:

- broad and narrow terms in the Liver related investigations, signs and symptoms SMQ (20000008)
- broad and narrow terms in the Cholestasis and jaundice of hepatic origin SMQ (20000009)
- broad and narrow terms in the Hepatitis non-infections SMQ (20000010)
- broad and narrow terms in the Hepatic failure, fibrosis and cirrhosis and other liver damage SMQ (20000013)
- narrow terms in the Liver-related coagulation and bleeding disturbances SMQ (20000015)

The percentage of patients with any 1 of the terms will be summarized in addition to the percentages for each MedDRA PT. The percentages of patients with potentially drug-related hepatic disorders that led to permanent study treatment discontinuation will be summarized similarly.

#### 6.12.4.4.2. Liver Enzyme and Bilirubin Lab Values

The liver enzyme measures (alanine aminotransferase [ALT], aspartate aminotransferase [AST], alkaline phosphatase [ALP], direct bilirubin, total bilirubin) will be summarized by treatment group. Postbaseline value and the change from baseline (last nonmissing value before randomization) to postbaseline value at Week 26 visit (planned tests) will be summarized for patients who have both a baseline and at least 1 postbaseline result, and compared between treatment groups by using ANCOVA model with the term of treatment and baseline value of the response variable. All analyses will be provided in SI units.

The last nonmissing observation at or prior to Week 26 (including early discontinuation visit) will also be analyzed by an ANCOVA model with the term of treatment, baseline value of response variable.

#### 6.12.4.4.3. Treatment-Emergent Elevation of Liver Enzyme Lab Values

The percentages of patients with the following elevations in hepatic laboratory tests at any time during the treatment period (0 to 26) will be summarized between treatment groups:

- The percentages of patients with postbaseline ALT measurement ≥3 times (3X), 5 times (5X), and 10 times (10X) the Covance upper limit of normal (ULN) will be summarized for all patients with a postbaseline value by the following baseline categories: ≤1X, >1X to <3X, ≥3X, missing.
- The percentages of patients with postbaseline AST measurement ≥3 times (3X), 5 times (5X), and 10 times (10X) the Covance ULN will be summarized for all patients with a postbaseline value by the following baseline categories: ≤1X, >1X to <3X, ≥3X, missing.
- The percentages of patients with postbaseline total bilirubin measurement ≥2 times (2X) the Covance ULN will be summarized for all patients with a postbaseline value by the following baseline categories: ≤1X, >1X to <2X, ≥2X, missing.

Baseline will be the maximum observation in the baseline period including the lead-in period. The maximum value will be the maximum value from the treatment period. Planned and unplanned tests will be included.

Graphical profiles of ALT, AST, total bilirubin, and ALP will be provided for patients with an ALT or AST  $\geq$ 3X ULN or total bilirubin  $\geq$ 2X ULN during the treatment period. A listing for these patients will also be provided, including the actual measurement of ALT, AST, ALP, and total bilirubin, the corresponding reference high limits, demographics, disposition, drug exposure and AEs. The review for these patients includes an assessment of the proximity of any ALT or AST elevation to any total bilirubin elevation, ALP levels, other potential causes, and the temporal association with events such as nausea, vomiting, anorexia, abdominal pain, or fatigue.

All patient data, regardless of whether on IP, will be used for the above analyses related to hepatobiliary events.

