9.4.6.1. Hepatic Safety Monitoring

If a study patient experiences elevated ALT \geq 3X ULN, ALP \geq 2X ULN, or elevated TBL \geq 2X ULN, liver testing (Appendix 4) should be repeated within 3 to 5 days, including ALT, AST, ALP, TBL, direct bilirubin, gamma-glutamyl transferase, and creatine kinase to confirm the abnormality and to determine if it is increasing or decreasing. If the abnormality persists or worsens, clinical and laboratory monitoring should be initiated by the investigator and in consultation with the study medical monitor. Monitoring of ALT, AST, TBL, and ALP should continue until levels normalize or return to approximate baseline levels.

Hepatic Safety Data Collection

Additional safety data should be collected via the CRF if 1 or more of the following conditions occur:

- o elevation of serum ALT to $\geq 5X$ ULN on 2 or more consecutive blood tests
- o elevated serum TBL to \geq 2X ULN (except for cases of known Gilbert's syndrome)
- o elevation of serum ALP to $\geq 2X$ ULN on 2 or more consecutive blood tests
- patient discontinued from treatment due to a hepatic event or abnormality of liver tests
- o hepatic event considered to be an SAE.

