10.3. Statistical Analyses

10.3.1. General Statistical Considerations

Statistical analysis of this study will be the responsibility of Lilly or its designee. Any change to the data analysis methods described in the protocol will require an amendment ONLY if it changes a principal feature of the protocol. Any other change to the data analysis methods described in the protocol, and the justification for making the change, will be described in the SAP or the clinical study report (CSR). Additional exploratory analyses of data will be conducted as deemed appropriate.

The primary analysis is for the treatment period through Week 26. The primary endpoint is the HbA1c measurement obtained at Week 26 (Visit 18).

Efficacy analyses will be conducted on all randomized patients using an intention-to-treat (ITT) approach according to the treatment the patients are assigned. Efficacy analyses, including the analyses for the primary and multiplicity adjusted objectives, will include data collected prior to permanent discontinuation of IP through Week 26. When change from baseline is included as a response variable of analysis models, the patient will be included in the analysis only if he/she has a baseline and a postbaseline measurement. Selected efficacy analyses will also be conducted using the Per-Protocol (PP) and Completer populations.

Safety analyses will be conducted on the Safety population. Analyses of AEs will include 2 sets of analyses, unless otherwise specified. The first set of analyses will include data collected prior to permanent discontinuation of IP. The second set of analyses will include all data collected during the course of the entire study regardless of IP use. Analyses of hypoglycemia will be conducted on data collected prior to permanent discontinuation of IP, while analyses for post-treatment may be conducted as needed. Analyses of safety laboratory measurements will be performed on all data collected during the planned treatment period regardless of IP use. Week 26 analyses will include treatment comparisons between the 2 treatment groups.

Unless otherwise noted, all tests of treatment effects will be conducted at a 2-sided alpha level of 0.05, and CIs will be calculated at 95%, 2-sided. All tests of interactions between treatment groups and other factors will be conducted at a 2-sided alpha level of 0.10.

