The definitions of baseline and postbaseline for the efficacy and safety analyses depend on which analysis period is being used. The following analysis periods will be used:

- Lead-in Period Visits 2-8
- 26-Week Treatment Period from randomization to Week 26 prior to discontinuation of IP
- 26-Week Treatment Period and Safety Follow-Up Visit from randomization to Visit 801 (including all data regardless of IP use)

The data on IP is defined based on the following rules:

- for data only measured at an office visit
  - MMTT postbaseline data will be considered as data on IP if the MMTT performance date is on or prior to the last IP dose date
  - Other postbaseline data (for example, vital signs, laboratory tests, and questionnaires) will be considered as data on IP if the measurement date is on or prior to the cutoff date defined as 14 days after the last IP dose date
- for data collected as running records with an exact date stamp such as adverse events (AEs) and diary entries where the dates of the measures were not tied with the date of an office visit, postbaseline data with dates ≤ (last study drug dose date +1) will be considered as data on IP.

Table 6.2 describes the rules for determining the patient population, baseline and postbaseline observations for the different analysis periods.

For continuous measures, summary statistics will include sample size, mean, SD, median, minimum, and maximum for both the actual and the change from baseline measurements. Least-squares (LS) means and standard errors derived from the analysis models will also be displayed. Treatment comparisons will be displayed showing the treatment difference LS means and the 95% CIs for the treatment differences, along with the p-values for the treatment comparisons.

For categorical measures, summary statistics will include sample size, frequency, and percentages. Fisher's exact test will be used for treatment comparisons.

For laboratory values, Systeme International (SI) units will be presented. Therefore, both % and mmol/mol will be presented for HbA1c and mmol/L will be presented for glucose measurements.

All baseline measures will be analyzed using an analysis of variance (ANOVA) model that has treatment as the model terms.

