Safety Laboratory Tests (chemistry, hematology, lipids) – continuous analysis	All Patients in the Safety Population with a baseline and a postbaseline observation	Last of Visits 1-8	Visit 18 (planned) AND Last of Visits 9-18 (planned including early discontinuation visits), regardless of IP use
Safety Laboratory Tests (chemistry, hematology, lipids) – categorical analysis	All Patients in the Safety Population with a normal baseline (with respect to the direction being analyzed) and a postbaseline observation	Visits 1 -8 (including unplanned tests)	Visits 9-18 (including unplanned tests), regardless of IP use

Study	Patient Population	Baseline Observations	Postbaseline Observations
Period/Analysis			
TEAEs	All patients in the Safety Population	Prior to first dose of randomized IP (or Visit 8 date if missing) and after the first dose of open-label insulin lispro (or Visit 2 date if missing)	From first dose of randomized IP to last dose of randomized IP AND From first dose of randomized IP to Visit 801
Hypoglycemia events	All patients in the Safety Population	All Visits 2-8	All Visits 9-18 prior to discontinuation of IP
Weight and vital signs	All Patients in the Safety Population with a baseline and a postbaseline observation	Last of Visits 2-8	Visits 9-18 prior to discontinuation of IP AND Visits 9-801 regardless of IP use
Anti-insulin lispro antibody	Safety Population	Visit 2	Visits 3-801 regardless of IP use

Baseline and Postbaseline Definitions and Patient Po	pulation by Study	v Period and Type of Analysis
Buschne und i ostbuschne Demittons und i utent i	pullution by Stud	j i ci ioù una i jpe oi i inaijsis

Abbreviations: 1,5-AG = 1,5-Anhydroglucitol; ANCOVA = analysis of covariance; EQ-5D-5L = European Quality

of Life- 5 Dimensions 5 Level; EQ-VAS = EuroQol visual analogue scale; HbA1c = hemoglobin A1c; IP = investigational product; ITSQ = Insulin Treatment Satisfaction Questionnaire; ITT = intention-to-treat; LOCF = last-observation-carried forward; MMTT = mixed meal tolerance test; MMRM = mixed-effect model repeated measures; SMBG = self-monitored blood glucose; TEAE = treatment-emergent adverse event; WPAI-GH = Work Productivity and Activity Impairment General Health.

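### For completers, repeat liver tests prompted by the Visit 18 panel fall outside the SAP's liver-elevation tables, so a later higher value can go uncounted

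*SAP*

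**What the plan says.** SAP 6.12.4.4.3 tabulates ALT and AST at or above 3, 5 and 10 times ULN, and total bilirubin at or above 2 times ULN. On the period, it says that these "elevations in hepatic laboratory tests at any time during the treatment period (0 to 26) will be summarized between treatment groups". On which value is graded: "The maximum value will be the maximum value from the treatment period. Planned and unplanned tests will be included". Graphical profiles and a listing are produced for patients who reach ALT or AST 3X or bilirubin 2X in the same period.

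SAP Table 6.2 has no separate liver row. Its row for categorical safety laboratory analyses sets the postbaseline window as "Visits 9-18 (including unplanned tests), regardless of IP use". Protocol 10.3.1 sets the same limit: "Analyses of safety laboratory measurements will be performed on all data collected during the planned treatment period regardless of IP use".

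On testing, the chemistry panel in the Schedule of Activities is marked at Visits 1, 8, 18 and early discontinuation only; Visit 801 has none. Under Protocol 9.4.6.1, when ALT reaches 3X, ALP 2X or total bilirubin 2X, "liver testing (Appendix 4) should be repeated within 3 to 5 days". If the abnormality persists or worsens, "Monitoring of ALT, AST, TBL, and ALP should continue until levels normalize or return to approximate baseline levels".

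SAP 6.1 also lists a longer analysis period, "26-Week Treatment Period and Safety Follow-Up Visit from randomization to Visit 801 (including all data regardless of IP use", and treats laboratory data dated up to 14 days after the last dose as on-IP data.

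**The concern.** How high an enzyme elevation goes, and whether bilirubin follows it, is often known only from the repeat tests. Here the scheduled test that would prompt those repeats in a completer is the last one inside the analysis window. The tables would then grade that patient on the Visit 18 value alone unless an unplanned test happened to be done earlier in treatment.

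Two things are at stake. A patient already counted at 3X may later reach 5X, 10X or bilirubin 2X without appearing in those rows. And a patient below all table cut-offs at Visit 18 may cross one on repeat and appear in no table, profile or listing of this section. The rows concerned are likely to hold few patients, so one or two missed cases could change how they read.

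**Working it through.** The plan states no figure for this point, so the check is a comparison of the schedule with the window, followed by day arithmetic.

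**1. Scheduled liver tests.** The marked columns of the chemistry row are Visits 1, 8, 18 and early discontinuation. A completer therefore has one scheduled post-randomization test, at Visit 18.

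**2. Timing of the repeat.** Inputs: Week 26, Visit 18 window of 7 days either side, repeat at 3 to 5 days.
- Week 26 = 26 × 7 = day 182.
- Repeat after a day-182 visit: 182 + 3 = day 185 to 182 + 5 = day 187, that is 185/7 = 26.4 to 187/7 = 26.7 weeks.
- Visit 801 is nominally 30 × 7 = day 210.

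**3. Inside or outside the tables?** This depends on how the end of the period is read.
- *By visit (Visits 9 to 18, Table 6.2):* any repeat prompted by the Visit 18 result is after Visit 18, so all are outside.
- *By a nominal day-182 cut-off:* Visit 18 may fall on days 175 to 189 (15 days) with 3 repeat intervals, giving 15 × 3 = 45 combinations. The repeat is on or before day 182 for 5 visit days at +3, 4 at +4 and 3 at +5: 5 + 4 + 3 = 12 of 45. These are combinations, not probabilities. Later monitoring would mostly still be outside.

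The sentence in 6.12.4.4.3 that all data are used whether or not the patient is on IP concerns IP use. It does not move the end of the period.

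**4. Are the excluded tests far from treatment?** Under Protocol 7.2.1.5 a completer's last dose is at Visit 18 or the evening before. With Visit 18 on day 182 the 14-day limit of SAP 6.1 is day 182 + 14 = 196, or 181 + 14 = 195. Repeats on days 185 to 187 are inside that limit. The SAP would thus class them as on-IP data, yet the visit window leaves them out.

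**5. Two hypothetical courses.**
- ALT 3.2X at Visit 18, 6X four days later, then 11X with bilirubin 2.3X at ten days. The tables show 3X only. The patient does trigger a profile and a listing.
- ALP at or above 2X at Visit 18, with ALT and AST below 3X and bilirubin below 2X. The protocol calls for a repeat. If ALT reaches 3X on that repeat, no table, profile or listing in 6.12.4.4.3 is triggered, because ALP is not a trigger there and the ALT value is after the window.

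**6. Size.** The documents give no liver-elevation rate. Assume 0.2% to 2% of the 298 planned completers (Protocol 10.1) have a repeat trigger at Visit 18:
- 298 × 0.002 = 0.6 patients; 298 × 0.02 = 6.0 patients.
- Chance of at least one such patient: 1 − (1 − 0.002)^298 = 0.45; 1 − (1 − 0.02)^298 = 0.998.

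Only those whose later value crosses a higher cut-off would change category, so these are upper figures for each assumed rate.

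**The case against.** The case for leaving the SAP alone has five parts.

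- *The window follows the protocol.* Protocol 10.3.1 limits safety laboratory analyses to the planned treatment period, and Protocol 10.3.4 runs safety analyses through Week 26. This stands. A reader might infer that the SAP contradicts the protocol; it does not. It is a gap in the window that both documents share.
- *Not every repeat is excluded.* A reader might infer that all protocol-required repeats are lost. The documents do not support that, since unplanned tests count. Repeats after an unplanned on-treatment test, after a Visit 8 trigger, or after an early discontinuation panel in a patient still followed can fall inside. The point is confined to completers' repeats prompted by Visit 18.
- *Under-grading is possible, not established.* A reader might also infer that liver peaks are systematically understated. That does not follow. The Visit 18 value is counted at its own grade, and a stable or falling repeat changes nothing. Nothing in the documents suggests a difference between arms.
- *Other displays limit the loss.* Patients at ALT or AST 3X or bilirubin 2X at Visit 18 get profiles, a listing and a review of how close enzyme and bilirubin elevations are. Hepatic adverse events run to Visit 801 (SAP Table 6.4). This largely stands for flagged patients, although the SAP does not say whether post-Visit 18 values are shown. It helps less with the ALP-only case: Protocol 9.4.5 requires a laboratory finding to be reported as an adverse event when it is clinically significant and results in a diagnosis, so an isolated rise need not appear there.
- *The added data are imperfect.* They are for-cause and collected after study insulin has stopped, and Protocol Appendix 4 allows local assay while the tables use the central laboratory's ULN. This stands and calls for labelling and care with reference limits. The 14-day rule weakens the off-treatment argument for the first repeat, but not for later monitoring.

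**Conclusion.** The point holds for completers. Under the Visits 9 to 18 definition, repeat and monitoring tests that follow an abnormal Visit 18 liver result are outside the ALT, AST and bilirubin threshold tables and cannot trigger a profile or listing. Later, higher values can therefore be missed in those tables. The sharpest gap is the patient below every table cut-off at Visit 18 who crosses one on repeat.

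The size is unknown and probably small: about 0.6 to 6 of 298 completers with a trigger under an assumed rate of 0.2% to 2%, and fewer who would change category. No primary or multiplicity-adjusted objective is affected. It is worth correcting because the rows are rare-event rows, the tests are ones the protocol already calls for, and the change is cheap. The conclusion rests on reading the end of the period by visit; under a strict day-182 reading a minority of first repeats would be included.

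**What to change.** In SAP 6.12.4.4.3:

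1. Keep the 0 to 26 week tables, which match the protocol.
2. Add a version of the ALT, AST and bilirubin tables over the period from randomization to Visit 801 already defined in SAP 6.1, with planned and unplanned tests regardless of IP use.
3. Apply the profile and listing trigger over that longer period, and state that profiles and listing show values after Visit 18.
4. Grade locally assayed results against the ULN of the laboratory that ran them.
5. Label the added version as containing for-cause, off-treatment values, so that it is not read as a second scheduled assessment.
6. Add a line to Table 6.2 saying how unplanned liver tests after Visit 18 are assigned.

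The cost is SAP wording, one further run of existing tables and a wider listing. No new visit or test is needed. The one practical demand is that local results reach the database with their reference limits. The change will not give untriggered completers more than their one scheduled test, since Visit 801 carries no chemistry panel.

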#### 6.12.5. Clinical Laboratory Evaluation

The data from safety laboratory measures will be summarized at Week 26 where the lab test is planned to be collected. Postbaseline and change from baseline to postbaseline for laboratory tests will be summarized for patients who have both baseline and at least 1 postbaseline result and compared between treatment groups by using ANCOVA model with the term of treatment and baseline value of the response variable. Analyses will be provided in SI units.

The last nonmissing observation at or prior to Week 26 (planned tests including early discontinuation) will also be analyzed by an ANCOVA model with the term of treatment, baseline value of the response variable.

The percentages of patients with treatment-emergent abnormal, high, or low laboratory results at any time during the treatment period (0 to 26) will be summarized for patients who have both baseline and at least 1 postbaseline result and compared between treatment groups using Fisher's exact tests. A treatment-emergent abnormal result is defined as a change from normal at all

baseline visits to abnormal at any time during the treatment period. A treatment-emergent high result is defined as a change from a value less than or equal to the high limit at all baseline visits to a value greater than the high limit at any time during the treatment period. A treatment-emergent low result is defined as a change from a value greater than or equal to the low limit at all baseline visits to a value less than the low limit at any time during the treatment period. A treatment-emergent visits to a value less than the low limit at any time during the treatment period. Planned and unplanned measurements will be included. **CC** be used to define the low and high limits. Only patients who have normal baseline values for the analysis being performed will be included in the analysis for treatment-emergence.

Liver enzymes measures will not be included in the above analyses as different analyses will be used as described in Section 6.12.4.4.2 and Section 6.12.4.4.3.

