8.1.1. Permanent Discontinuation from Study Treatment

Patients will be discontinued from the IP in the following circumstances:

- The investigator may decide that the patient should stop IP. If this decision is made because of an AE, SAE, or a clinically significant laboratory value, the study drug is discontinued for that patient and appropriate measures are to be taken. Lilly or its designee is to be alerted.
- The patient requests to discontinue IP.
- If the patient becomes pregnant.
- If an investigator, study site personnel performing assessments, or patient is unblinded, the patient must discontinue IP.
- If the patient, for any reason, requires treatment with another therapeutic regimen or therapeutic agent that has been demonstrated to be effective for treatment of the study indication. Discontinuation from IP should occur prior to introduction of the new agent.
- Use of prohibited concomitant medication (see Table ITSD.8).
- If the patient has not taken IP for more than 14 consecutive days.
- **Discontinuation due to a hepatic event or liver test abnormality.** Patients who are discontinued from investigational product due to a hepatic event or liver test abnormality should have additional hepatic safety data collected via CRF.

Discontinuation of the investigational product for abnormal liver tests **should be** considered by the investigator when a patient meets one of the following conditions after consultation with the Lilly designated medical monitor:

- alanine aminotransferase (ALT) or aspartate aminotransferase (AST) >8X upper limit of normal (ULN)
- ALT or AST >5X ULN for more than 2 weeks
- ALT or AST >3X ULN and total bilirubin level (TBL) >2X ULN or international normalized ratio (INR) >1.5
- ALT or AST >3X ULN with the appearance of fatigue, nausea, vomiting, right upper-quadrant pain or tenderness, fever, rash, and/or eosinophilia (>5%)
- alkaline phosphatase (ALP) >3X ULN
- ALP >2.5X ULN and TBL >2X ULN
- ALP >2.5X ULN with the appearance of fatigue, nausea, vomiting, right quadrant pain or tenderness, fever, rash, and/or eosinophilia (>5%)

Patients discontinuing from the investigational product prematurely for any reason should complete adverse event and other follow-up procedures per Section 2 (Schedule of Activities), Section 9.2 (Adverse Events), and Section 9.4 (Safety) of this protocol.

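### SAP 6.12.5 removes alkaline phosphatase and direct bilirubin from the treatment-emergent laboratory tables, but 6.12.4.4.3 gives them no replacement threshold or patient-selection rule

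*SAP*

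**What the plan says.** Three SAP sections have to be read together.

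- Section 6.12.4.4.2 lists the analytes: "The liver enzyme measures (alanine aminotransferase [ALT], aspartate aminotransferase [AST], alkaline phosphatase [ALP], direct bilirubin, total bilirubin) will be summarized by treatment group". It plans summaries of value and change at Week 26 (planned tests), a last-observation analysis, and ANCOVA for each.
- Section 6.12.4.4.3 gives percentages of patients above multiples of the upper limit of normal (ULN) for ALT and AST (3X, 5X, 10X) and total bilirubin (2X), by baseline category, counting planned and unplanned tests. It continues: "Graphical profiles of ALT, AST, total bilirubin, and ALP will be provided for patients with an ALT or AST" at or above 3X ULN, or total bilirubin at or above 2X ULN. The listing covers the same patients. ALP is shown for them but selects nobody.
- Section 6.12.5 defines the treatment-emergent abnormal, high and low tables for laboratory tests in general, then adds: "Liver enzymes measures will not be included in the above analyses as different analyses will be used", citing the two sections above.

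The protocol uses ALP at patient level. Under section 9.4.6.1, ALP of at least 2X ULN is one of three findings after which "liver testing (Appendix 4) should be repeated within 3 to 5 days". The same section asks for extra hepatic data on "elevation of serum ALP to" at least 2X ULN on two or more consecutive tests. Section 8.1.1 lists seven liver conditions under which stopping the study drug is to be "considered by the investigator when a patient meets one of the following conditions". Three of them involve ALP, including "alkaline phosphatase (ALP) >3X ULN" and "ALP >2.5X ULN and TBL >2X ULN".

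**The concern.** The exclusion in section 6.12.5 rests on the liver tests being analysed elsewhere. For ALT, AST and total bilirubin that is true. For ALP and direct bilirubin the categorical part of the replacement does not exist, so they leave one table and enter no other.

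A cholestatic pattern would be expected to show as a few patients with large ALP rises. A safety reader would want the number of such patients in each arm and the course of each one. As written, the plan supplies neither. Baseline matters as well: exclusion criterion 20 screens on total bilirubin, ALT and AST but not on ALP, so patients can enter with a raised value, and later elevations need to be read against baseline category.

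**Working it through.** The plan states no figure on this point. The check sets the protocol's rules against the SAP's selection rule, then looks at what the remaining analyses can show.

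**1. Which protocol conditions does the SAP rule select?** The rule in section 6.12.4.4.3 is ALT or AST ≥3X ULN, or total bilirubin (TBL) ≥2X ULN.

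| Protocol 8.1.1 condition (multiples of ULN) | Selected by SAP rule? |
|---|---|
| ALT or AST >8X | Yes |
| ALT or AST >5X, over 2 weeks | Yes |
| ALT or AST >3X, with TBL >2X or INR >1.5 | Yes |
| ALT or AST >3X, with symptoms or eosinophilia | Yes |
| ALP >3X | No, unless another test is raised |
| ALP >2.5X with TBL >2X | Yes, through TBL |
| ALP >2.5X, with symptoms or eosinophilia | No, unless another test is raised |

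Five of the seven are always selected and two are not. Example patients with ALT, AST and TBL all at 1X ULN give the same answer: ALP at 2.0X, at 3.1X, and at 2.6X with symptoms are none of them selected. ALP at 2.6X with TBL at 2.1X is selected, through TBL. Of the three re-test triggers in protocol 9.4.6.1 (ALT, ALP, TBL), only ALP has no counterpart in the SAP rule.

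**2. What do the means show?** Assume 350/2 = 175 patients per arm and, since the documents give no ALP distribution, a baseline ALP of 0.5X to 1.0X ULN in the affected patients. If k patients rise to 3.1X, the arm mean moves by k × (3.1 − baseline)/175.

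- k = 1: 2.1/175 = 0.012 to 2.6/175 = 0.015X ULN
- k = 5: 10.5/175 = 0.060 to 13.0/175 = 0.074X ULN

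The ANCOVA would be insensitive to a handful of such patients.

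**3. What do the other summary statistics show?** SAP 6.1 also requires SD, median, minimum and maximum for continuous measures. One extreme value at a planned visit would set the arm's maximum and raise its SD. It would not say whether one patient or several were affected, and the results are in SI units, not multiples of ULN.

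**4. Which tests enter?** SAP Table 6.2 restricts the continuous analysis to planned tests, including early discontinuation. The Schedule of Activities plans post-randomization chemistry only at Visit 18 and early discontinuation. A higher value found only at an unplanned test, such as the 3-to-5-day re-test, is therefore outside the continuous analysis. Section 6.12.4.4.3 does take unplanned tests, but has no ALP row.

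**5. Does another display catch it?** The categorical laboratory row in Table 6.2 does not, because section 6.12.5 removes the liver tests from that analysis. The hepatic term search in section 6.12.4.4.1 works on reported adverse events. Protocol 9.4.5 asks for laboratory findings to be reported as adverse events when they are clinically significant and lead to a diagnosis, so an isolated ALP rise may never become one.

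**The case against.** The strongest reply is that ALP is far from ignored. It has by-arm summaries with SD and maximum, an ANCOVA at Week 26 and at last observation, and a place in the profiles and listing of every patient selected on ALT, AST or total bilirubin. A high value reported as an adverse event reaches the hepatic term search. If the study drug is stopped because of an adverse event, the case also reaches the discontinuation tables and the narratives. SAP 6.1 allows further exploratory analyses. Nor does the SAP set out to mirror the protocol's cut-offs: the protocol uses ALT or AST >8X ULN where the SAP tabulates 10X. Direct bilirubin has no threshold anywhere in the protocol, and total bilirubin has its own row. The adverse effects that protocol 3.3 associates with treprostinil include no hepatic event.

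All of this stands, and it limits the weight of the point. It does not supply the missing categorical analysis. The adverse-event route is conditional, the maximum is not a count, and an optional later analysis is not a planned one. The text redacted in section 6.12.5 concerns the source of the laboratory limits, so it does not explain the omission, and section 6.12.4.4.3 shows no redaction.

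Several stronger readings are tempting, and the documents do not support them:

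- That only mean change is reported for ALP. SAP 6.1 requires more.
- That a single ALP of 2X ULN calls for the extra hepatic data. It calls for a re-test; the ALP criterion for extra data needs two or more consecutive tests.
- That ALP forces discontinuation. The protocol leaves this to the investigator's consideration after consulting the medical monitor.
- That all three ALP conditions go unseen. The one combined with bilirubin is selected through bilirubin.
- That the report could not give the number of patients. The count is unplanned, but it can be obtained from the chemistry data.

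**Conclusion.** The gap is real and minor. Section 6.12.5 justifies an exclusion by pointing to analyses that, for ALP and direct bilirubin, have no categorical part. No by-arm count of ALP or direct bilirubin elevations is planned, and an isolated ALP rise that meets the protocol's re-test rule, or either of two of its seven conditions for considering discontinuation, selects no patient for a profile or the liver listing.

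For direct bilirubin, the conclusion rests on taking the list in section 6.12.4.4.2 as the meaning of liver enzyme measures in section 6.12.5. ALP is covered on any reading. The sizes in step 2 rest on the assumed baseline range and are illustrations, not estimates of how often such rises will occur. No primary, multiplicity-adjusted or other secondary endpoint is affected.

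**What to change.** Change the SAP reporting text only; no clinical rule needs to change.

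1. In section 6.12.5, limit the exclusion to the analytes that section 6.12.4.4.3 covers. Direct bilirubin then stays in the treatment-emergent high table, as does ALP if step 2 is not adopted.
2. In section 6.12.4.4.3, add a row for postbaseline ALP at multiples the protocol already uses, at least ≥2X and >3X ULN, by baseline category (for example ≤1X, >1X to <2X, ≥2X, missing). Count unplanned tests, as for the other rows, and state how a re-test taken after Visit 18 is assigned to a period.
3. In the same section, add ALP ≥2X ULN to the criteria that select patients for the profiles and the listing.

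Both analytes are already in the chemistry panel in protocol Appendix 2, so no new samples or visits are needed. The cost is a few table rows and some programming.
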